4.7 STUDY DISCONTINUATION

This study may be terminated by Rush University Medical Center at any time.

Reasons for terminating the study may include the following:

- The incidence or severity of adverse events in this or other studies indicates a potential health hazard to subjects
- Subject enrollment is unsatisfactory
- Data recording is inaccurate or incomplete

4.8 STATISTICAL METHODS

4.8.1 Analysis of the Conduct of the Study

There is no formal sample size calculation in this pilot study. As this is a phase I/II study, a sample size of 10 patients is chosen, making sure that it is feasible financially to conduct the study and logically to complete the study within 12 months. If and when the study is planned for a phase II randomized control trial, appropriate statistical analysis will be determined.

- **4.8.2 Safety Analyses**

Any adverse events, laboratory assessments, physical examinations, vital signs, ocular examinations and measurements from all 10 subjects will be utilized to summarize safety data for this pilot study.

- **4.8.3 Efficacy Analyses**

As this is a small pilot study, no formal statistical analyses are planned

- a. **Primary Endpoint**

- The percentage change of the area measured in pixels of the patient's neovascularization as measured by Optomap FA fluorescein angiography
 - The percentage change of macular edema measured by retinal thickness by OCT

- b. **Secondary Endpoints**

- Mean change in Best Corrected Visual Acuity (BCVA), as assessed by the number of letters read correctly on the ETDRS eye chart at a starting test distance of 4 meters, at 3 and 6 months

- Percentage of patients gaining 3 or more lines of vision according to ETDRS eye chart testing
- Occurrence rate of proliferative diabetic complications including vitreous hemorrhage, iris neovascularization and tractional retinal detachment

4.8.4 Missing Data

Analyses of efficacy and safety will be based on available cases, without imputation for missing values.

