3. STUDY DESIGN

3.1 DESCRIPTION OF THE STUDY

This is an open-label, Phase I/II study of intravitreally-administered ranibizumab in subjects with persistent (greater than three months) diabetic neovascularization previously treated with panretinal photocoagulation (at least 1200 or more 500- μ m burns).

Consented, enrolled subjects will either receive open-label intravitreal injections of 0.5-mg dose of ranibizumab or additional panretinal photocoagulation (up to 500 300-500 μ m laser spots) in a ratio of two-to-one (2:1) at the beginning of the study period. ETDRS best-corrected visual acuity, contrast sensitivity, and Optos color photography will be performed at enrollment, at weeks 1, 2, 3 and 4, and at months 2, 3, 4, 5 and 6. The subjects will undergo fluorescein angiography utilizing the Optomap FA (fluorescein angiography) system and optical coherence tomography (OCT) at enrollment, at weeks 2 and 4, and at months 2, 3, 4 and 6. The subjects will be followed for a 6-month period for stabilization, regression, or recurrence of

neovascularization. In addition, patients will be evaluated for occurrence of macular edema.

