4.5.2 Early Termination Assessments

Subjects who withdraw from the study prior to completion should return for an early termination evaluation 14 days (\pm 7 days) following the last injection/study visit for monitoring of all adverse events (serious and nonserious). The schedule of assessments for early termination is the same as that for the final visit.

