4.6 SUBJECT DISCONTINUATION

Subjects have a right to withdraw from the study at any time.

The subject may be withdrawn from the study for any reasons: if it is in the best interest of the subject, intercurrent illness, adverse events, or worsening

condition. Rush University Medical Center may request the withdrawal of a subject because of protocol violations, administrative reasons, or any other valid and ethical reasons.

Subjects will be discontinued and receive standard additional panretinal photocoagulation for development of neovascular glaucoma (NVG).

Other reasons for subject discontinuation may include, but are not limited to, the following:

- Sensory rhegmatogenous retinal detachment or Stage 3 or 4 macular hole
- Investigator determination that it is not in the best interest of the subject to continue participation
- Pregnancy
- Verteporfin PDT treatment in the study eye
- Pegaptanib sodium injection treatment in either eye
- SAE
- Any other safety concerns

If a subject discontinues or is discontinued from the study, he or she will not be allowed to re-enter the study.

In the event of an adverse event in the study eye that is considered by the investigator to be severe in intensity, serious consideration should be given to discontinuing the subject from the study.

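### Mandatory discontinuation for neovascular glaucoma ends scheduled follow-up, so the available-case BCVA means at 3 and 6 months can omit patients because they progressed

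*Protocol*

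**What the plan says.** Protocol 4.6 makes one discontinuation rule mandatory: "Subjects will be discontinued and receive standard additional panretinal photocoagulation for development of neovascular glaucoma (NVG"). The other reasons listed there are ones that may lead to discontinuation. The same section adds: "If a subject discontinues or is discontinued from the study, he or she will not be allowed to re-enter the study".

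What remains is set in Protocol 4.5.2: "Subjects who withdraw from the study prior to completion should return for an early termination evaluation 14 days", with a tolerance of 7 days either way, counted from the last injection or study visit. That visit repeats the final-visit assessments, and Appendix A shows BCVA among them. Although 4.5.2 speaks of withdrawal, 5.1 applies the evaluation to subjects who discontinue early, so NVG cases are covered. The further contact described in 5.1 collects adverse events only.

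On the analysis side, Protocol 4.8.3 lists as a secondary endpoint the mean change in BCVA, measured by "letters read correctly on the ETDRS eye chart at a starting test distance of 4 meters, at 3 and 6 months". Protocol 4.8.4 sets the rule for absent values: "Analyses of efficacy and safety will be based on available cases, without imputation for missing values".

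Study treatment is given once, at enrollment (4.3.2, 4.5.1). Section 4.2 assigns 7 patients to ranibizumab and 3 to PRP. Section 4.8.3 plans no formal statistical analyses.

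**The concern.** Together these rules make absence from the later BCVA summaries depend on the outcome. A patient leaves scheduled follow-up because the eye got worse, and the available-case mean is then taken over those who did not leave for that reason. If patients with NVG see worse than the others in their arm, the reported late mean is too favourable for that arm.

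The source of the problem is the conduct rule in 4.6. Available-case summaries are ordinary in a small descriptive pilot, and 4.8.4 would do little harm if the visits took place. Because treatment is a single session at enrollment, ending the visits stops no study drug, and rescue PRP can be given without ending them. This also cannot be left to a statistical analysis plan, which can decide how to use values but cannot create assessments that were not made.

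At stake is the reading of a secondary visual-acuity summary in arms of 7 and 3, where one patient is 14% or 33% of an arm.

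**Working it through.** **Inputs.** Arm sizes are 7 and 3 (4.2). Post-baseline BCVA visits are weeks 1, 2, 3 and 4 and months 2, 3, 4, 5 and 6 (4.5.1). The early-termination visit is at the last visit + 14 ± 7 days (4.5.2). BCVA change is summarised at months 3 and 6 (4.8.3). Assumed: 30-day months, NVG found at a scheduled visit, and the deficit d in letters.

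**Arm split.** Repeating ranibizumab, ranibizumab, PRP over 10 patients gives 7 and 3, as stated.

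**Scheduled visits not held.** Nine post-baseline visits are planned, 8 of them before month 6.
- NVG found at week 1, 2, 3 or 4 or at month 2 (5 of the 8): neither the month-3 nor the month-6 visit is held.
- NVG found at month 3, 4 or 5 (3 of the 8): month 3 is kept and the month-6 visit is not held.

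These are counts of visits, not of risk. Four of the first five fall within the first month.

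**Can the early-termination BCVA stand in?**
- NVG at month 5 (day 150): the visit falls on day 157 to 171, which is 9 to 23 days before day 180.
- NVG at month 2 (day 60): the visit falls on day 67 to 81, which is 9 to 23 days before day 90 but 99 to 113 days before day 180.
- NVG at month 4 (day 120): the visit falls on day 127 to 141, which is 39 to 53 days before day 180.

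A visit window could assign the month-5 case to month 6, and the month-2 case to month 3. For earlier NVG the visit is far from month 6. It may also come after the rescue PRP.

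**Effect on an arm mean.** Let the other n − 1 patients have mean change m, and the omitted patient m − d. The mean of all n is [(n − 1)m + (m − d)]/n = m − d/n. The available-case mean is m, so it is overstated by d/n.

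| Assumed d (letters) | Ranibizumab, d/7 | PRP, d/3 | Shift in ranibizumab − PRP, one loss in each arm: d/7 − d/3 = −4d/21 |
|---|---|---|---|
| 5 | 0.7 | 1.7 | −1.0 |
| 15 | 2.1 | 5.0 | −2.9 |
| 30 | 4.3 | 10.0 | −5.7 |

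One omission moves the PRP mean 7/3 = 2.3 times as far as the ranibizumab mean, so one loss in each arm does not cancel.

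**How often.** The protocol gives no NVG rate. If the 6-month risk were 5%, 10% or 20%, the same in both arms and independent between patients, the chance of at least one case among 10 would be 1 − 0.95^10 = 40%, 1 − 0.90^10 = 65% or 1 − 0.80^10 = 89%. These risks are assumptions only.

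**The case against.** The strongest reply is that the effect is narrow and its size is assumed. The primary efficacy measures are neovascular area and retinal thickness. BCVA is secondary and descriptive, no test is planned, and with 10 patients a single NVG discontinuation is visible in a listing. Sampling noise is also much larger: with an assumed SD of 15 letters, the standard error of a 7-versus-3 difference is 15 × √(1/7 + 1/3) = 10.4 letters, against a 2.9-letter shift from one loss in each arm at d = 15. All of this stands and lowers the weight. It does not remove the fault, because the omission is systematic and cheap to prevent.

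A reader might infer more than the documents support:
- **Every NVG case before month 6 loses its 6-month value.** This assumes a windowing rule that is not shown. The early-termination BCVA after NVG at month 5 might be used for month 6.
- **NVG itself goes unrecorded.** It does not. The endpoint "Occurrence rate of proliferative diabetic complications including vitreous hemorrhage, iris neovascularization and tractional retinal detachment" is open-ended and names iris neovascularization, and 4.8.2 summarises adverse events and ocular examinations from all 10 subjects.
- **The rule contradicts 3.1.** That section says "The subjects will be followed for a 6-month period for stabilization, regression, or recurrence of" neovascularization, which describes planned follow-up. A discontinuation rule is an ordinary exception to it.
- **The 3-line gain is inflated.** The endpoint "Percentage of patients gaining 3 or more lines of vision according to ETDRS eye chart testing" has no stated time point or denominator, so no effect on it can be shown.
- **The primary measures are biased.** Their visits stop too, but nothing in the documents shows a shift in either.

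**Conclusion.** The point holds in limited form. Followed as written, 4.6 with 4.5.2 and 4.8.4 can remove patients from the descriptive BCVA means at 3 and 6 months because they progressed. It does so most clearly when NVG comes early, since the only remaining visit is then far from month 6.

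The size rests on assumptions. One omitted patient overstates the arm mean by d/7 or d/3, which is 0.7 to 4.3 letters (ranibizumab) or 1.7 to 10.0 letters (PRP) for d from 5 to 30. The direction requires that the patient with NVG does worse than the rest of the arm. If no patient develops NVG, or the early-termination value is windowed to the endpoint visit, the omission does not arise. The weight is minor to moderate, and the case for acting is that the remedy is cheap and unheld visits cannot be recovered later.

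**What to change.** In Protocol 4.6, state that discontinuation for NVG, with rescue PRP given exactly as now, does not end the scheduled assessments through month 6 unless the patient withdraws consent. At the least, BCVA at months 3 and 6 should be kept. Beside the BCVA summaries, label values taken after rescue as such, and report the number of NVG discontinuations by arm.

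The cost is a few continued visits in a study of 10 patients, with matching consent text. There is also a cost in interpretation: rescue PRP is the comparator treatment, so post-rescue values in the ranibizumab arm no longer reflect ranibizumab alone. The label lets readers separate the two. Patient care and the timing of rescue do not change. There is no need to score NVG as a failure to gain lines, since that convention could misclassify a rescued patient who does gain.

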4.8.5 Interim Analyses

No formal schedule of interim analyses is planned. Reports of adverse events from this extension study may be reviewed and summarized periodically while the study is ongoing to ensure the safety of subjects.

4.9 DATA QUALITY ASSURANCE

Accurate, consistent, and reliable data will be ensured through the use of standard practices and procedures.

5. ASSESSMENT OF SAFETY

The safety of ranibizumab will be assessed through the collection and analysis of any adverse events that occur during the study whether related to the study drug or not.

5.1 ADVERSE EVENTS

AEs that start on Day 0 through the last study visit will be recorded on the appropriate AE pages of the CRF. Subjects discontinuing early from the study should return for an early termination evaluation and will be contacted 7 days after their last injection or study visit to elicit for occurrence of adverse events (serious and nonserious).

For this protocol, an AE is any "on study" untoward medical occurrence (e.g., sign, symptom, disease, syndrome, intercurrent illness) that occurs in a study subject, regardless of the suspected cause. "On study" refers to Day 0 through the last study visit.

Unchanged, chronic conditions are NOT AEs and should not be recorded on the AE pages of the CRF. An exacerbation or worsening of a chronic condition should be recorded as an AE.

Both serious and nonserious AEs should be graded on a three-point scale (mild, moderate, severe) and reported in detail on the appropriate AE page of the CRF.

The suggested definitions are as follows:

Mild: Discomfort noticed but no disruption of normal daily activity

Moderate: Discomfort sufficient to reduce or affect normal daily activity

Severe: Incapacitating with inability to work or perform normal daily activity

Using the following criteria, investigators also need to assess whether there is a reasonable possibility that study drug caused or contributed to the AE.

- Yes (possibly or probably)

There is a clinically plausible time sequence between onset of the AE and study drug administration; and/or

There is a biologically plausible mechanism for study drug causing or contributing to the AE; and

The AE may or may not be attributed to concurrent/underlying illness, other drugs, or procedures.

- No

A clinically plausible temporal sequence is inconsistent with the onset of the AE and study drug administration; and/or

A causal relationship is considered biologically implausible.

5.2 BASELINE MEDICAL CONDITIONS

It is not necessary to complete an AE CRF page for chronic medical conditions present at enrollment that do not worsen in intensity or frequency during the trial. These medical conditions should be adequately documented on the appropriate page of the CRF (medical history and/or physical examination). However, medical conditions present at enrollment that worsen in intensity or frequency during the treatment or post-treatment periods and ongoing AEs that started during the previous study should be reported and recorded as AEs.

5.3 EVALUATIONS

Reviews of body systems will be performed.

Ophthalmologic evaluations will include slit lamp examination, dilated binocular indirect high-magnification ophthalmoscopy, measurements of BCVA and intraocular pressure, and finger-count testing. (See Section 4.5 for a detailed description of the study assessments.)

5.4 VITAL SIGNS

Pulse, blood pressure, respiration, and temperature will be measured at protocol-specified study visits (see Section 4.5).

5.5 PROCEDURES FOR RECORDING AND REPORTING ADVERSE EVENTS

• 5.5.1 Recording Adverse Events (see examples below)

To improve the quality and precision of acquired AE data, investigators should observe the following guidelines:

- Whenever possible, use recognized medical terms when recording AEs on the AE pages of the CRF. Do not use colloquialisms and/or abbreviations.
- If known, record the diagnosis (i.e., disease or syndrome) rather than component signs and symptoms on AE pages of the CRF (e.g., record congestive heart failure rather than dyspnea, rales, and cyanosis). However, signs and symptoms that are considered unrelated to an encountered syndrome or disease should be recorded as individual AEs on the CRF (e.g., if congestive heart failure and severe headache are observed at the same time, each event should be recorded as an individual AE).
- AEs occurring secondary to other events (e.g., sequelae) should be identified by the primary cause. A “primary” AE, if clearly identifiable, generally represents the most accurate clinical term to record on AE pages of the CRF. If a primary serious AE (SAE) is recorded on an SAE CRF, events occurring secondary to the primary event should be described in the narrative description of the case.

For example:

Orthostatic hypotension → Fainting and fall to floor → Head trauma → Neck pain

The primary AE is orthostatic hypotension.

- **5.5.2 Serious Adverse Events**

An AE occurring **at any dose** (including overdose) should be classified as **SERIOUS** if:

- It resulted in death (i.e., the AE caused or led to death).
- It was life threatening (i.e., the AE placed the subject at immediate risk of death; it does not apply to an AE that hypothetically might have caused death if it were more severe).
- It required or prolonged inpatient hospitalization (i.e., the AE required at least a 24-hour inpatient hospitalization or prolonged a hospitalization beyond the expected length of stay; hospitalizations for elective medical/surgical procedures, scheduled treatments, or routine check-ups are not SAEs by this criterion).
- It was disabling (i.e., the AE resulted in a substantial disruption of the subject's ability to carry out normal life functions).
- It resulted in a congenital anomaly/birth defect (i.e., an adverse outcome in a child or fetus of a subject exposed to the molecule or study drug prior to conception or during pregnancy).
- It does not meet any of the above serious criteria but may jeopardize the subject or may require medical or surgical intervention to prevent one of the outcomes listed above.

SAE Reporting

Investigators must report all SAEs to Genentech within 48 hours of observing or learning of the event. For initial SAE reports, investigators should record all case details that can be gathered within 48 hours on the SAE page of the CRF.

The completed SAE page and SAE Fax Cover Sheet should be faxed immediately upon completion to the Genentech Drug Safety at:

[contact]

or

[contact]

Relevant follow-up information should be submitted to Genentech as soon as it becomes available.

- **5.5.3 Special Reporting Situations**

- a. **Death**

Death is an outcome of an event. The **event** that resulted in the death should be recorded and reported on the SAE pages of the CRF.

- b. **Hospitalizations for Surgical or Diagnostic Procedures**

The **illness** leading to the surgical or diagnostic procedure should be recorded as the SAE, not the procedure itself. The procedure should be captured in the case narrative as part of the action taken in response to the illness.

- c. **Pregnancy**

- **5.5.4 Type And Duration Of Follow-Up After Adverse Events**

All reported AEs should be followed until resolution or until the subject's participation in the study ends. Subjects who have an ongoing study drug-related SAE at study completion or at discontinuation from the study will be followed by the investigator or his or her designee until the event is resolved or determined to be irreversible, chronic, or stable by the investigator.

- **5.5.5 Regulatory Reporting Requirements for Principal Investigators Holding Their Own INDs**

Investigators conducting studies under their own INDs are responsible for expedited Safety Reports and IND Annual Reports to the FDA.

Expedited IND Safety Reports:

For this **Investigator Sponsored IND Study**, some additional reporting requirements for the FDA apply in accordance with the guidance set forth in 21 CFR § 312.32.

Events meeting the following criteria should be submitted to the Food and Drug Administration (FDA) as expedited IND Safety Reports according to the following guidance and timelines:

Fatal or Life-Threatening, Unexpected, Drug-related SAEs

The Investigator is required to notify the FDA of any **fatal or life-threatening** adverse event that is **unexpected** and assessed by the investigator to be **related** to the use of ranibizumab. Reports are to be telephoned or faxed to the FDA **within 7 calendar days** of the Investigator's knowledge of the event. Additionally, notify Genentech Medical Science Liaison by telephone **within 7** calendar days.

An **unexpected** adverse event is one that is not already described in the ranibizumab Investigator's Brochure (IB). This includes adverse events that have not been identified as life-threatening or causing a death as described in the IB, for example, elevated hepatic enzymes or hepatitis versus liver failure. This also includes unusual AEs not specifically described in the IB, for example, hemorrhage versus intraocular bleeding.

The 7-day telephone or fax report must be followed within 8 additional calendar days by a written IND safety report (MedWatch 3500A Form). Written IND Safety Reports should include an Analysis of Similar Events in accordance with regulation 21 CFR § 312.32. (See Appendix D for Analysis of Similar Events template). All safety reports previously filed to the IND concerning similar events should be analyzed. The significance of the new report in light of the previous, similar reports should be commented on.

Written IND safety reports with Analysis of Similar Events are to be submitted to the FDA, Genentech, the IRB, and all participating investigators within 15 calendar days of the

Investigator's knowledge of the event. The FDA prefers these reports on a MedWatch 3500A Form but alternative formats are acceptable (e.g. summary letter).

FDA Fax Number for IND Safety Reports:

1 [contact]

All written IND Safety Reports submitted to the FDA by the Investigator must also be faxed to:

Genentech Medical Science Liaison:

Name: [name]
[contact] or [contact]
[contact]

AND:

Genentech Drug Safety at:

[contact] or [contact]

AND:

Institutional Review Board:

Research and Clinical Trials Administration Office
Rush University Medical Center
[name]
[name]
[contact]
[contact]

For questions related to Safety reporting, contact your Genentech Medical Science Liaison.

Serious, Unexpected, and Drug-related SAEs (not life-threatening or fatal)

A written IND Safety Report (described above) should also be produced for any unexpected SAE that is considered related to the use of ranibizumab but is not life-threatening or fatal. Investigators are required to notify the FDA, Genentech, the IRB, and all participating investigators by submitting the IND Safety Report within 15 days of the Investigator's knowledge of the event.

IND Annual Reports

All IND annual reports submitted to the FDA by the Investigator should be copied to Genentech. Copies of such reports should be mailed to:

[name]
Director of Drug Safety
[name]
Genentech, Inc.
[name]
[name]

- **5.5.5.1 MedWatch 3500A Reporting Guidelines: (See Appendix C for MedWatch form)**

In addition to completing appropriate patient demographic and suspect medication information, the report should include the following information within the Event Description (section 5) of the MedWatch 3500A form:

- Identification of the primary event term
- Protocol description (and number, if assigned)
- Description of event, severity, treatment, and outcome if known
- Supportive laboratory results and diagnostics
- Investigator's assessment of the relationship of the adverse event to each investigational product and suspect medication
- If a death occurred, autopsy results if available

MedWatch forms can be obtained on-line at www.fda.gov/medwatch or by calling the FDA at [name].

- **Follow-up information:**

Additional information may be added to a previously submitted report by any of the following methods:

- Add to the original MedWatch 3500A report and submit it as follow-up
- Add documents and submit as follow-up with the original MedWatch 3500A form
- Summarize new information and fax it with a cover letter including subject identifiers (i.e. D.O.B. initial, subject number), protocol description and number, if assigned, brief adverse event description, and notation that additional or follow-up information is being submitted. (Patient identifiers are important so that new information is added to the correct initial report.)

Occasionally Genentech may contact the investigator for additional information, clarification, or current status of the subject for whom an adverse event was reported.

For questions regarding SAE reporting, you may contact the Genentech Medical Science Liaison.

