3.4 SAFETY PLAN

The safety assessments to be conducted for this study are listed in Section 4.5 and Appendix A.

- Potential adverse events include but are not limited to local injection site reaction, subconjunctival hemorrhage, vitreous hemorrhage, retinal tear or detachment or endophthalmitis.
- If a patient has an occurrence of retinal tear or detachment or endophthalmitis:
 - The patient will not be included in the study
 - Treatment will be based on the event and at the discretion of the treating physician based on current accepted practice standards
 - Any necessary testing such as ultrasound or cultures will be performed as indicated by the specific event.
 - Any necessary procedures, such as vitreous tap and injection, laser for tears or surgical repair of detachments will be performed according to current practice standards

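### Follow-up of serious adverse events beyond the end of participation is tied to study drug alone, so no PRP-arm event can qualify and injection-procedure events depend on how the investigator reads the causality criteria

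*Protocol*

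**What the plan says.** Section 5.5.4 has two rules. The general one covers both arms and any cause: "All reported AEs should be followed until resolution or until the subject's participation in the study ends". The second extends follow-up beyond that point, but only for one class of event: "Subjects who have an ongoing study drug-related SAE at study completion or at discontinuation from the study will be followed by the investigator" or a designee, until the event resolves or is judged irreversible, chronic or stable.

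What counts as related is settled in section 5.1: "investigators also need to assess whether there is a reasonable possibility that study drug caused or contributed to the AE". The Yes rating begins with timing: "There is a clinically plausible time sequence between onset of the AE and study drug administration; and/or" a biologically plausible mechanism. It then adds: "The AE may or may not be attributed to concurrent/underlying illness, other drugs, or procedures". The No rating begins: "A clinically plausible temporal sequence is inconsistent with the onset of the AE and study drug administration; and/or" a causal link is thought biologically implausible. There is no category for the injection procedure or for PRP.

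Section 3.4 lists the anticipated risks: "Potential adverse events include but are not limited to local injection site reaction, subconjunctival hemorrhage, vitreous hemorrhage, retinal tear or detachment or endophthalmitis". It then says that a patient with a retinal tear, detachment or endophthalmitis will not be included in the study. Section 4.6 names SAEs and rhegmatogenous detachment among the possible reasons for discontinuation.

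Section 4.2 allocates 7 patients to ranibizumab and 3 to additional PRP. Section 4.3.2 gives ranibizumab only to the ranibizumab group, and the footnote to Appendix A confirms that each patient gets one treatment or the other.

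**The concern.** The study compares two assigned treatments, and section 3.3.1 makes ocular and other adverse events a primary outcome. The rule on who is followed after exit recognises only one of those treatments. A serious complication of study laser that is unresolved at exit carries no protocol duty of further follow-up, while an equally serious event rated as related to ranibizumab does.

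Within the ranibizumab arm, several of the risks in 3.4 arise from putting a needle into the eye, and Appendix B treats endophthalmitis as a risk of intravitreal injection. Asking only about the drug leaves the investigator to decide whether the needle counts as part of it.

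At stake is the final outcome of the gravest ocular events. These are the events most likely to take a patient out of the study while still unresolved.

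**Working it through.** **Allocation.** Section 4.2 alternates two ranibizumab (R) and one PRP (P). Over ten patients the sequence is R R P, R R P, R R P, R. That gives 7 R and 3 P, matching the protocol's own figure. The PRP share is 3/10 = 30%.

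**Can a PRP-arm SAE qualify under 5.5.4?**
- The condition requires the SAE to be related to study drug.
- Throughout 4.3 and 5, study drug means ranibizumab: 4.3 describes only its vials and storage, and 5 states that the safety of ranibizumab is being assessed.
- PRP patients receive none (4.3.2, Appendix A), and no crossover is described.
- With no study drug administration there is no time sequence to it and no mechanism by which it could act. Only No is available, so 0 of 3 patients can qualify.

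**Can an injection-procedure SAE qualify?** Let T = plausible timing after study drug administration and B = plausible biological mechanism for the drug (1 = present, 0 = absent). The third Yes condition, on other causes, is met whichever way attribution falls. Hence:
- Yes = T or B
- No = (not T) or (not B)

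| T | B | Meets Yes | Meets No |
|---|---|---|---|
| 1 | 1 | yes | no |
| 1 | 0 | yes | yes |
| 0 | 1 | yes | yes |
| 0 | 0 | no | yes |

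An endophthalmitis or detachment soon after the injection, attributed to the needle rather than the molecule, falls in the second row. It satisfies both definitions, and the protocol has no rule for choosing between them.

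**When does this matter?** Until participation ends, both arms are under the same rule. The two arms part only for an SAE still ongoing at that moment:
- For patients who complete, that means an SAE unresolved at month 6.
- For patients removed early under 3.4 or 4.6, participation may end while the event is active. What remains is an early termination evaluation at 14 ± 7 days (4.5.2) and a contact at 7 days (5.1), both timed from the last injection or study visit. Neither is designed to follow an event to its outcome.

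The protocol gives no SAE rate, so the number of patients affected cannot be estimated. In the PRP arm it lies between 0 and 3.

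**The case against.** The strongest reply is that the Yes criteria already cover procedures. An event that follows the injection in plausible time can be rated related even if attributed to a procedure, so a sensible investigator would keep following it. That stands as far as it goes, and it means injection-procedure events are not excluded from extended follow-up. It does not remove the overlap with No, and it does nothing for the PRP arm.

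A reader might go further than the text allows in four ways:
- *Events rated unrelated are lost.* They are not. Sections 5 and 5.1 collect all on-study adverse events whatever the cause, 5.5.2 sends all SAEs to the manufacturer within 48 hours, and 4.8.2 summarises safety data from all 10 subjects.
- *Serious events are followed to resolution in one arm only.* The general rule in 5.5.4 applies to both arms until resolution or the end of participation. Only the period afterwards differs.
- *Safety cannot be compared between arms.* The primary safety outcome is incidence and severity, recorded from Day 0 through the last study visit on the same visit schedule in both arms. It does not depend on the relatedness rating.
- *The number of procedure-type risks listed in 3.4 measures the gap.* It does not. Extended follow-up concerns SAEs only, and an injection site reaction or subconjunctival hemorrhage counts only if it meets a seriousness criterion in 5.5.2.

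It is also fair to say that 3.4 provides for testing and treatment of tear, detachment and endophthalmitis. That covers care of the patient, but does not require the outcome to be followed and recorded for the study.

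**Conclusion.** The point holds in a limited form. On the literal text, 3 of 10 patients (30%) can never qualify for SAE follow-up beyond participation, although they receive an assigned study treatment. For the other 7, extended follow-up of an injection-procedure SAE turns on which of two overlapping definitions the investigator applies. What can be lost, unequally between arms, is the final outcome of SAEs ongoing at exit.

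This rests on three assumptions: study drug means ranibizumab, PRP patients receive no ranibizumab while on study, and removal under 3.4 or 4.6 can end participation. The text supports the first directly. The second follows from the allocation and the absence of any crossover. The third is the natural reading of those sections, but should be made explicit.

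The sponsor should make the change: the rule is stated, it treats the arms differently for no given reason, and it is cheap to correct.

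**What to change.** - In 5.1, have relatedness rated to the assigned study treatment, recorded separately for ranibizumab, the injection procedure and study PRP.
- In 5.5.4, replace *study drug-related SAE* with *SAE related to study drug, injection procedure or study PRP*.
- Reconcile 3.4 with 5.1 and 5.5.4, so that it is clear what safety follow-up applies to a patient who leaves the study because of a tear, detachment or endophthalmitis, in either arm.
- Leave the expedited reporting criteria in 5.5.5 tied to ranibizumab.

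The cost is amendment wording and two more tick boxes on the AE page. The downside is occasional longer follow-up of an SAE, in at most 10 patients. No treatment changes.
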